**Table 2. Additional Adverse Events** 

Event	Assessment/Criteria	Action
Participant reports		Normal school protocols (as outlined by the
elevated suicide risk to	School Counsellor is	Protecting and Supporting Children and Young
school	notified and assessed	People Policy) are followed.
Participant reports	participant's risk	
depressed mood to	using normal school	School Counsellor to report these events to the
school	protocols.	trial manager via phone call or email.
Participant reports		
anxiety to school		The trial manager asks school counsellor about
Risk of significant harm		any adverse events upon 6 week follow-up
as identified by school		
contact		The research team will report to the Outcomes
		Advisory Group at 2-week intervals on the total
		number of trigger emails being sent.

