## **Type of Endpoint**

Efficacy/Safety: to measure the intervention's influence on help-seeking for depression, anxiety and stress; and to show that the intervention is safe under conditions of the proposed protocol.

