- 4. Monitoring and Feedback. At two points in the study (Day 15 and Day 22) participants received an automated 18-item "monitoring questionnaire" to assess how they were doing. This consisted of the Goldberg Depression and Anxiety Scales and was delivered via email or SMS. An automated thank you message was received alongside a reminder to use the program if participants completed this questionnaire.
- 5. Reassessment (Post-test/endpoint): At Day 43, researchers revisited the schools. Participants again logged onto the service using the same URL and unique ID codes and were delivered the final endpoint questionnaires. In theory, the results of these questionnaires would be used to determine whether a participant had responded to care or needed to be "stepped up". In accordance with the Clinical Practice Guidelines for the Treatment of Depression in Young Adults, if a participant has not responded to their care within 43 days of their baseline allocation, they would be "stepped up" to the next level of care. See Table 3 below for the stepping matrix at 43 days. The matrix was designed such that a participant would not be stepped down, instead will either remain at the same step or step up. However, as the current trial ceased at 43 days, no stepping occurred during this trial. Instead, this trial was

designed to provide the clinical data necessary to determine whether the steps are feasible for future trials.

Throughout the trial, participants will be obligated to use Smooth Sailing at pre-test (for registration and baseline measure collection) and again at post-test (for reassessment and final endpoint collection) only. Completion of the monitoring questionnaires and use of the other components is entirely voluntary, and will be a measured as part of the study.

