# **Assessment of Safety**

#### **Outcomes Advisory Group**

An Outcomes Advisory Group has been established to provide specific monitoring, governance, and reporting of adverse events and trial safety. This group consists of the trial manager, the lead investigators, and the medical expert. This team meets every two weeks, and on an as-needed basis, to monitor the safety of the trial. A data safety monitoring board will not be utilised in the current study. This decision was made on the basis of two key factors:

- 1. The current study targets a non-clinical population, and does not target a high risk sample.
- 2. The research platform used in the trial has an alert system which provides timely feedback to research personnel, so that distressed participants can be identified and attended to straight away. Once identified, school counsellors will be made aware of the distressed participant, so that they may provide immediate and, if necessary, ongoing assistance. This procedure ensures the highest level of care for participants, as school counsellors are appropriately trained, familiar, accessible, and available to assist should such a scenario eventuate.

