## Procedure for responding to risk of significant harm within this Trial

Within the Smooth Sailing service, the pre-test and post-test assessments include the Patient Health Questionnaire (PHQ-9). This questionnaire is used to assess the presence of depression symptoms and has one item assessing suicidal risk (item 9). This item reads "Over the past two weeks, have you had any thoughts that you would be better off dead or of hurting yourself in some way". A participant is able to answer either 'not at all' (0); 'several days' (1), 'more than half the days' (2) or 'nearly every day' (3). The battery also includes the General Anxiety Disorder Questionnaire (GAD-7) which is used to screen for the presence of general anxiety symptoms. Both the PHQ-9 and GAD-7 are standardised psychological screening measures and as such, may provide an objective measure of anxiety, depression, and suicide risk if completed truthfully. However, further assessment from a trained mental health professional is required for the extent of an individual's risk to be fully determined. As such, the most appropriate response to elevated scores is to notify a trained mental health professional so that they can follow up with the participant. This is a commonly accepted protocol for mental health research studies. In the context of this study, the trained mental health professional will be the School Counsellor.

Given the sensitive nature of the questionnaires, students must be provided with adequate supervision for completion. In the current study, any student participating in the trial will be subject to the following supervisory conditions:

• Students will only be able to complete the questionnaires during class time, under the supervision of the researcher, school counsellor and/or class teacher. This will ensure that the student has adequate supervision, and if an alert is triggered, the school

- counsellor will be able to make timely contact. This will also ensure that the research team will be able to monitor the impacts of this questionnaire more precisely. Any student who cannot attend school for the class period in which the baseline and follow-up questionnaires are to be completed will not be able to participate in the study.
- A trained mental health researcher from the Black Dog Institute will be present at the
  school during class time for the completion of the baseline and follow-up

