**Table 1. Potential Adverse Events** 

Event	Assessment/Criteria	Action
"Moderately	A Patient Health	An automatic email alert will be sent to the
severe" or "severe"	Questionnaire-9 (PHQ-9)	nominated school counsellor and a member
depression at	baseline score of 15 or	of the research team. The school counsellor
baseline	above.	will be notified to follow-up with the
"Moderately	A Generalised Anxiety	participant using normal school protocols,
severe" or "severe"	Disorder (GAD-7)	including any mandatory reporting
anxiety at baseline	baseline score of 15 or	requirements. The trial manager will also re-
	above.	contact the school counsellor within 48

		hours to confirm that the email notification was received and is being acted upon. The research team will report to the outcomes advisory group at 2-week intervals on the total number of alerts.
Suicidal ideation at baseline	A score greater than or equal to one on the PHQ-9 item 9.	As above. In addition, a pop-up alert is shown to the participant which states the following: "Thanks for letting us know. We think it'd be great if you could tell a trusted adult about how you have been feeling. If you're not up to talking to someone you know, try Kids Helpline on [name] (it's not just for kids!) or Lifeline [name]. Smooth Sailing will let your School Counsellor know that it's been tough for you lately. Your School Counsellor will touch base with you in the next few days, just to see if there is anything they can do to help. Don't worry - this is all done very privately. In the meantime, keep using Smooth Sailing - we're here to help!"In addition, the participant will automatically receive access to the Smooth Sailing program which includes a range of psycho-education, help-seeking resources, and online therapy programs, which are evidence-based. Participants have access to this program for the duration of the trial.

Please see the supplementary material "Responding to risk of harm" document for a more detailed outline and flowcharts for decision making regarding risk of harm in the current trial.

Table 2 outlines additional adverse events during the trial which are not captured by the assessments and our action.

[figure not shown]

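### The fortnightly safety report for Table 2 adverse events is a count of trigger emails, which by the protocol's own definitions includes none of those events

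*Protocol*

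**What the plan says.** The protocol's section Summary of Potential Adverse Events divides adverse events between two tables. (The Intervention section has its own Tables 1 and 2, on step allocation and care. They are not the ones meant here.)

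- **Table 1 (Potential Adverse Events)** covers what the questionnaires can detect. The text above it says these events are monitored through the number of emails that the service triggers. The table ties the automatic alert to a PHQ-9 score of 15 or more, a GAD-7 score of 15 or more, or a score of at least 1 on PHQ-9 item 9. The total number of alerts goes to the Outcomes Advisory Group every two weeks.
- **Table 2 (Additional Adverse Events)** covers the rest. It is introduced with the sentence "Table 2 outlines additional adverse events during the trial which are not captured by the assessments and our action". Its rows are elevated suicide risk reported to the school, depressed mood reported to the school, anxiety reported to the school, and risk of significant harm identified by the school contact.

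The action column of Table 2 contains three reporting steps. First, "School Counsellor to report these events to the" trial manager, by phone or email. Second, the trial manager asks the counsellor about "any adverse events upon 6 week follow-up". Third, the research team reports to the Outcomes Advisory Group every two weeks on the total "number of trigger emails being sent".

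The section Outcomes Advisory Group says that the group was established "to provide specific monitoring, governance, and reporting of adverse events and trial safety", and that no data safety monitoring board will be used.

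**The concern.** The third step does not follow from the first two. Steps one and two collect the Table 2 events from the people who see them, the school counsellors. Step three then reports a different quantity, the output of the automated alert system, which belongs to Table 1. The wording is so close to the Table 1 reporting line that it was probably carried across.

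The consequence concerns what the oversight group is formally given. Under Type of Endpoint, one aim is "to show that the intervention is safe under conditions of the proposed protocol", and the Inclusion Criteria admit adolescents with current or past suicidality. Table 2 holds the disclosures that reach the school rather than the questionnaire, including elevated suicide risk. If the written rule is followed, the prescribed figure does not respond to how many of these disclosures there are, and any safety tally built from that figure would leave them out.

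**Working it through.** No arithmetic on sample size, error rates or event rates is involved, and the protocol gives no figure to reproduce. The check is whether the quantity reported can contain the events it is reported for.

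**1. What a trigger email is.** Summary of Potential Adverse Events describes email triggers as sent by the service, for events that the assessments may capture. Table 1 (Potential Adverse Events) gives the thresholds at baseline. The section Procedure for responding to risk of significant harm within this Trial applies notification for moderately severe or severe scores at follow-up as well. In each case the source is a questionnaire score.

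**2. What a Table 2 event is.** By the introductory sentence, it is an event that the assessments do not capture. By the criteria column, it becomes known because the counsellor is notified and assesses the student under normal school procedures. No questionnaire score is involved.

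**3. Putting 1 and 2 together.** An email is sent only on a score, and a Table 2 event is one that is not registered by a score. Each Table 2 event therefore adds 0 to the count.

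| Table 2 event | How it becomes known | Counted in trigger emails? |
|---|---|---|
| Elevated suicide risk reported to school | Counsellor | No |
| Depressed mood reported to school | Counsellor | No |
| Anxiety reported to school | Counsellor | No |
| Risk of significant harm identified by school contact | Counsellor | No |

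Result: 0 of 4 event types are included. With *k* Table 2 events in a fortnight, their contribution to the report is *k* × 0 = 0 for any *k*.

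**4. Overlap of students.** A student may both score above a threshold and disclose to the school. The email then records the score. It does not record the disclosure, so overlap does not turn the email count into a count of Table 2 events.

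**5. Whether the right count is available.** It is. The first two steps in the same action column deliver the events to the trial manager.

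**The case against.** The strongest reply is that the group has another route to the information. Counsellors report to the trial manager, the trial manager is a member of the Outcomes Advisory Group, and the group meets every two weeks and as needed. Table 2 does not say that the email count is all the group receives, and no stopping rule or threshold in the protocol uses that number. This stands, and it limits the consequence. A reader might infer that the group is blind to these events, that they go unrecorded, or that students go without follow-up. The documents do not support any of that: the events are collected, and students are handled under school policy. What remains is that no written step has the events counted or reported to the group, and the only report that is written down is of something else.

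Secondly, trigger emails might mean the counsellors' emails to the trial manager. The protocol uses the term for messages sent by the service. Even on the other reading, events reported by phone would be missed, as would those first disclosed when the counsellor is asked at 6 weeks.

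Thirdly, the protocol refers to a supplementary document on responding to risk of harm, which is not at hand and may add a reporting step. If so, the group's information would be more complete, but the sentence in Table 2 would still name the wrong quantity.

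Finally, a reader might go further and calculate how many whole fortnights between the Day 1 and Day 43 assessments must show no alerts at all. The documents do not support that calculation. It needs the monitoring questionnaires in between to raise no alert. The Intervention section says "An automated thank you message was received alongside a reminder to use the program if participants completed this questionnaire", but it does not say that nothing else can follow. A trial-wide figure would also need all schools to start in one common two-week window. The recruitment text does not fix such a window across schools, and the Trial Schedule, with pre-test in February and post-test in June 2017, makes it doubtful. Nor is the calculation needed, since the email count omits Table 2 events in every interval, with or without alerts.

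**Conclusion.** The point holds as a contradiction within the protocol. The fortnightly figure specified for Table 2 events counts 0 of the 4 event types, whatever their number. This rests on two readings, both taken from the protocol's own wording: trigger emails are the service's automatic alerts on assessment scores, and Table 2 events are those that the assessments do not capture. No event rate is given or assumed, so the number of events that would be left out cannot be stated.

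The scope is narrow. The defect lies in the reported figure, not in care, in ascertainment or in the Table 1 alert count, and no efficacy result is affected. It should still be corrected, because this is the stated safety report to the trial's only oversight body, it covers suicide risk in a school-age population, and it is wrong as written rather than detail left to another document.

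**What to change.** In the action column of Table 2 (Additional Adverse Events), replace the trigger-email sentence with wording such as:

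*Every two weeks, the research team will report to the Outcomes Advisory Group the number and type of Table 2 events that school counsellors have reported to the trial manager (elevated suicide risk, depressed mood, anxiety, risk of significant harm). Events first disclosed at the 6-week question will be added to the final safety tally.*

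Leave the Table 1 alert count as it is, and present the two counts separately.

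The cost is one sentence and a few extra lines in an existing report, filled from calls and emails that counsellors already make. No new data collection is needed. The drawbacks are a small tallying effort and the possibility that the same student appears in both counts, so the two should not be summed as if they were distinct students.

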# **Statistics**

Although this study is an uncontrolled acceptability trial, we will be examining differences pre and post-test. A recent systematic review of help-seeking interventions (Gulliver et al 2012) reports an effect size of d = 0.12 - 0.53 for psycho-education interventions. As such, our sample size calculations are based on using an alpha of 0.05 and effect size of 0.50. As guided by Cohen (1992), 64 participants are needed to demonstrate this effect. Given that 40% are likely to drop out, we will target 106 participants for recruitment.

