# **Trial Design**

## **Study Type**

An uncontrolled, non-randomised, one arm pre-post interventional trial.

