#### **Analysis**

Data will be collected using the Black Dog Institute e-health platform. Participant data will then be exported to SPSS statistical software for analyses. Statistical analyses will be performed using SPSS 21.0 (SPSS Inc., Chicago, II, USA). The primary outcome measures will be analysed using mixed modelling which is similar to repeated-measures analysis. This type of analysis will determine any significant differences in the scores reported at time 1 (pre) and then at time 2 (post). The primary hypothesis will be evaluated by differences in pre and post scores on help-seeking questionnaires. Secondary hypotheses will be evaluated by descriptive analyses of the acceptability and feasibility questionnaires.

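### The required 64 matches the per-group size of a two-group comparison, so it does not describe what this one-arm pre-post analysis can detect

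*Protocol*

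**What the plan says.** The Study Type section describes the trial as "An uncontrolled, non-randomised, one arm pre-post interventional trial". The Statistics section says "we will be examining differences pre and post-test". The Analysis section says "The primary outcome measures will be analysed using mixed modelling which is similar to repeated-measures analysis", and then "The primary hypothesis will be evaluated by differences in pre and post scores on help-seeking questionnaires". The comparison to be powered is therefore a change within the same students.

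For its size, the Statistics section cites a systematic review that "reports an effect size of d = 0.12 - 0.53 for psycho-education interventions" and continues that "our sample size calculations are based on using an alpha of 0.05 and effect size of 0.50". It then says, on the guidance of a published power reference, that "64 participants are needed to demonstrate this effect. Given that 40% are likely to drop out, we will target 106 participants for recruitment".

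The section gives no power, sidedness, pre-post correlation or SD of change. It does not say whether 0.50 is measured in SDs of the score (d) or SDs of the change (dz). The Recruitment, Screening & Consenting section adds that each school contributes a class of about 30 students.

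**The concern.** The number needed to detect a given effect depends on the design. In a two-group comparison the error comes from differences between people in both groups. In a pre-post comparison it comes from the SD of each person's change, which depends on the correlation between the two measurements. A figure taken from one design does not carry over to the other unless that correlation is stated.

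The 64 is the protocol's only statement of what the trial can detect. If it belongs to another design, a reader cannot tell from it what a null result would rule out, and an ethics committee cannot tell why this many adolescents are being enrolled.

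**Working it through.** **Inputs.** From the Statistics section: effect 0.50, alpha 0.05, 64 needed, 40% dropout, 106 recruited, cited range d = 0.12 to 0.53. Assumed, because the protocol does not state them: 80% power, a two-sided test, and pre-post correlations r of 0 to 0.7.

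**1. Reproducing 64.** For a two-group t-test, n per group is about 2(1.960 + 0.842)²/d² = 2 × 7.85/0.25 = 62.8. The exact t calculation gives 63.8, so 64 per group, or 128 in total. At 90% power it is 85 to 86 per group; one-sided at 80% power it is 50. Only the 80%, two-sided version gives 64.

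**2. Paired test, 0.50 read as standardised change (dz).** n is about (1.960 + 0.842)²/dz² = 7.85/0.25 = 31.4. The exact t calculation gives 33.4, so 34 completers; at 90% power it is 44. A paired test reaches about 64 at dz = 0.50 only if power is set near 97.5%.

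**3. Paired test, 0.50 read in score-SD units (d).** Convert with dz = d/√(2(1 − r)). Results with independent students:

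| r | dz for d = 0.50 | Completers for 80% power | Power with 64 at d = 0.50 |
|---|---|---|---|
| 0 | 0.354 | 65 | 79.5% |
| 0.3 | 0.423 | 46 | 91% |
| 0.5 | 0.500 | 34 | 98% |
| 0.7 | 0.645 | 21 | over 99% |

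**4. What 64 completers can detect.** At 80% power the smallest detectable dz is 0.356. In score-SD units this is 0.356 × √(2(1 − r)), which is 0.42, 0.36 or 0.28 at r = 0.3, 0.5 or 0.7. Over the same correlations, power is 13% to 23% at d = 0.12 and 91% to over 99% at d = 0.50.

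**5. Recruitment by class.** A class of 30 with 40% dropout leaves 30 × 0.6 = 18 completers. With an assumed intraclass correlation (ICC) of change, the design effect is 1 + 17 × ICC:
- ICC 0.01: 1.17; 64/1.17 = 54.7, effective size about 55, detectable dz about 0.39.
- ICC 0.05: 1.85; 64/1.85 = 34.6, effective size about 35, detectable dz about 0.49.

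Power at dz = 0.50 falls from 98% to about 95% and 81% respectively.

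**6. Dropout.** 64/0.60 = 106.7, which rounds up to 107. Expected completers are 106 × 0.6 = 63.6 against 107 × 0.6 = 64.2.

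**The case against.** The two-group origin is inferred. The protocol states neither power nor sidedness, and its power reference is not at hand. A paired calculation with d = 0.50 in score-SD units and r = 0 gives 65, almost the same number. This stands as a caution: the origin is a match, not a documented fact. It does not rescue the statement, because the protocol does not assume zero correlation, and repeated scores from the same students six weeks apart would ordinarily be positively correlated.

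The mismatch is also conservative. Under independence 64 completers give 98% power at dz = 0.50, and no endpoint, analysis or recruitment decision changes. This stands too, and it limits the severity.

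Two stronger readings are tempting. A reader might infer that the trial needs 128 students, or is underpowered for 0.50. The documents do not support this: there is no second group, and under independence 64 meets or exceeds the paired requirement at any clearly positive correlation. A reader might also take the low power at 0.12 as an error. It is not: the protocol discloses the range, 0.50 lies inside it, and choosing from it is a planning decision. Nor can one power figure be attached to 0.12. Entering d directly as dz gives 16%, but that silently assumes r = 0.5.

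**Conclusion.** The point holds, as a should-fix. The stated requirement of 64 matches a two-group formula and is not tied to the one-arm pre-post comparison that the protocol plans. At 80% power, two-sided, the paired requirement is 34 completers if 0.50 is a standardised change. In score-SD units it runs from 65 down to 21 as the correlation rises from 0 to 0.7. These figures rest on the assumed power, sidedness and correlations, and on independent students.

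The error is on the safe side for 0.50 under independence. That margin should not be taken as assured, since clustering within classes could move the detectable dz from 0.36 to between 0.39 and 0.49 at the ICCs illustrated, and the documents give no ICC. The rounding to 106 costs less than one expected completer and carries no weight in this conclusion.

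**What to change.** Keep the recruitment target and rewrite the basis in the Statistics section:

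- Name the calculation as a paired (pre-post) comparison, and state the power, the sidedness, whether 0.50 is d or dz, and the assumed pre-post correlation.
- Give the change detectable with 64 completers: dz = 0.36 at 80% power under independence, or 0.42, 0.36 or 0.28 score SD at correlations of 0.3, 0.5 or 0.7.
- Give power over the cited range as ranges across those correlations: 13% to 23% at d = 0.12 and 91% to over 99% at d = 0.50.
- Say that these figures treat students as independent, and give the values under an assumed ICC: effective size about 55 to 35 and detectable dz about 0.39 to 0.49 for ICC 0.01 to 0.05 with about 18 completers per class.
- As a minor correction, give the inflated number as 107. The Recruitment section lists recruitment status as completed, so this may be a correction of the record only.

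The cost is one paragraph of protocol text and at most one more participant. No endpoint or analysis changes.
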